10. STUDY DRUG MATERIALS AND MANAGEMENT

10.1 Study Drugs

Ketalar (ketamine hydrochloride injection) will be purchased from PAR Sterile Products, [name]. It will be provided as IV infusion administration.

The Investigational Product (IP) is a capsule intended for oral administration. Each capsule contains DCS and lurasidone hydrochloride. Inactive ingredients include mannitol, croscarmellose sodium, silica dioxide, and magnesium stearate.

10.2. Packaging and Labeling

Medication will be supplied in 23 cc wide mouth HDPE bottles with screw top closure. Each bottle will contain 2 capsules, the required dose for either morning or evening administration, and desiccant to aid stability. The bottles will be packaged into a cardboard kit containing 2 bottles for each day. Six different kit types will be available. Kit 1 will contain a 5-day titration pack with 10 bottles, each containing 2 capsules, for the first 5 days of the study. Kits 2 to 5 will contain 3-day step-up or step-down packs with 6 bottles, each containing 2 capsules. Kit 6 will contain a 7-day preferred dose pack with 14 bottles, each containing 2 capsules. A description of the 6 kit types is provided in Table 7.

Table 7 NRX-101 Kits

Kit Type	Day	Morning Dose		Evening Dose		Total Dose	
		DCS	Lurasidone	DCS	Lurasidone	DCS	Lurasidone
1 (7 Days)	1	350	16.5	0	16.5	350	33
	2	475	16.5	0	16.5	475	33
	3	350	16.5	350	33	700	49.5
	4	350	16.5	475	33	825	49.5
	5	475	33	475	33	950	66
	6	475	33	475	33	950	66
	7	475	33	475	33	950	66
2 (3 Days)	Uptitration for Agitation						
	step 1	475	33	475	66	950	99
3 (3 Days)	step 2	475	66	475	66	950	132
4 (3 Days)	Stepdown for Somnolence						
	step 1	350	16.5	475	33	825	49.5
	5 (3 Days)	step 2	350	16.5	350	16.5	700
6 (7 Days)	Preferred Dose	475	33	475	33	950	66

The composition and physical description of each capsule is below (Table 8 through Table 11) Investigational Product (NRX-101) Identification

Table 8 Active Capsule Composition and Physical Description

Strength	237.5/8.25	237.5/16.5	237.5/33	175/8.25	175/16.6	0/8.25
Size	0e1	0e1	0e1	0	0	0
Color	Light Blue	Swedish Orange	White	Light Blue	Swedish Orange	Light Blue
d-Cycloserine	242.1 mg / 39.69%	242.1 mg / 39.69%	242.1 mg / 39.69%	178.4 mg / 33.66%	178.4 mg / 33.66%	0 mg / 0%
Lurasidone	8.27 mg / 1.56%	16.55 mg / 3.12%	33.10 mg / 6.25%	8.27 mg / 1.56%	16.55 mg / 3.12%	8.27 mg / 2.07%
Mannitol 50C	311.03 mg / 50.99%	302.75 mg / 49.63%	286.20 mg / 46.92%	300.93 mg / 56.78%	292.65 mg / 55.22%	359.17 mg / 89.79%
Croscarmellose Sodium	39.50 mg / 6.48%	39.50 mg / 6.48%	39.50 mg / 6.48%	34.45 mg / 6.50%	34.45 mg / 6.50%	26.00 mg / 6.50%
Hydroxypropylmethyl cellulose E5 (6% solution)	0 mg / 0%	0 mg / 0%	0 mg / 0%	0 mg / 0%	0 mg / 0%	4.56 mg / 1.14%
Silica Dioxide	6.1 mg / 1.0%	6.1 mg / 1.0%	6.1 mg / 1.0%	5.30 mg / 1.0%	5.30 mg / 1.0%	0 mg / 0%
Magnesium Stearate	3.00 mg / 0.49%	3.00 mg / 0.49%	3.0 mg / 0.49%	2.65 mg / 0.50%	2.65 mg / 0.50%	2.00 mg / 0.50%
Total	610.0 mg / 100%	610.0 mg / 100%	610.0 mg / 100%	530.0 mg / 100%	530.0 mg / 100%	400.0 mg / 100%

Table 9 Lurasidone Capsule Composition and Physical Description

Strength	0/8.25	0/16.5	0/33	0/8.25	0/16.6
Size	0el	0el	0el	0	0
Color	Light Blue	Swedish Orange	White	Light Blue	Swedish Orange
Lurasidone	8.27 mg / 1.80%	16.55 mg / 3.60%	33.10 mg / 7.20%	8.27 mg / 2.07%	16.55 mg / 4.14%
Mannitol 50C	414.29 mg / 90.06%	406.01 mg / 88.26%	389.46 mg / 84.67%	359.17 mg / 89.79%	350.89 mg / 87.72%
Croscarmellose Sodium	29.90 mg / 6.50%	29.90 mg / 6.50%	29.90 mg / 6.50%	26.00 mg / 6.50%	26.00 mg / 6.50%
Hydroxypropylmethyl cellulose E5 (6% solution)	5.24 mg / 1.14%	5.24 mg / 1.14%	5.24 mg / 1.14%	4.56 mg / 1.14%	4.56 mg / 1.14%
Magnesium Stearate	2.30 mg / 0.50 %	2.30 mg / 0.50 %	2.30 mg / 0.50 %	2.00 mg / 0.50%	2.00 mg / 0.50%
Total	460 mg / 100%	460 mg / 100%	460 mg / 100%	400.0 mg / 100%	400.0 mg / 100%

Table 10 Placebo Capsule Composition and Physical Description

Strength	0/0	0/0	0/0	0/0	0/0
Size	0el	0el	0el	0	0
Color	Light Blue	Swedish Orange	White	Light Blue	Swedish Orange
Mannitol 50C					
Croscarmellose Sodium					
Hydroxypropylmethyl cellulose E5 (6% solution)					
Magnesium Stearate					
Total					

The NRX-101 capsule is supplied in 5 strengths as described below. Matching placebos containing either 8.25, 16.5, or 33 mg of lurasidone and no d-cycloserine (DCS) will also be supplied as well as a full placebo containing no DCS or lurasidone.

Table 11 Investigational Product (NRX-101) Identification

D-cycloserine (mg)	Lurasidone (mg)	Capsule Color	Capsule Size
237.5	33	White	OEL
237.5	16.5	Swedish Orange	OEL
237.5	8.25	Light Blue	OEL
175	16.6	Swedish Orange	0
175	8.25	Light Blue	0

Each IP formulation label will include the following information:

- Name of sponsor and address
- Protocol number
- Quantity of capsules
- Storage conditions
- Investigational drug statement (for clinical trial use only)
- Drug packager lot number
- Kit/Medication number
- Contents
- Administration statement
- Spaces for Study Coordinator to insert:
 - Subject number
 - Date Dispensed

When the study drug bottle is dispensed to a subject, the second panel of the label or a copy should be detached and affixed to the drug accountability page in the subject's study source document.

Sites will enter the subject screening ID number into the Randomization Page of the IVRS system, and the subject will be assigned to one of the three treatment groups. The bottle number Medication ID generated by the IVRS for each subject will be noted in the Randomization Page. Drug for each treatment day will be dispensed in 2 bottles each containing 2 capsules. Subjects will be instructed to take two capsules, each morning and evening.

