4.7 Dosing Rationale

The doses chosen for the three components of the sequential therapy are based on current dosing recommendations for each. In Stage 1, the one-time IV infusion of ketamine on Day 0 at 0.5 mg/kg over 40 minutes is below the lowest recommended IV concentration (1 mg/kg) to induce anesthesia, and is consistent with studies of ketamine for use in depression.

DCS is well-tolerated as a second-line treatment for TB at therapeutic split daily oral doses in the range of 500 to 1000 mg/day. The recommended oral dose of lurasidone for the treatment of acute depressive BD is 20 to 120 mg/day for up to 6 weeks. Therefore, dosing of the fixed-dose combination NRX 101 during Stage 2 will be twice daily over 6 weeks. The starting doses at 350 mg DCS and 16.5 mg lurasidone, and the titration over 5 days to a maximum of 950 mg DCS and 66 mg lurasidone are planned accordingly. Up-titration is built in to the dosing strategy in the case of subject agitation and a stepdown is allowed for somnolence.

For complete details regarding dosing recommendations, please see the product safety labeling for each of the drugs, which are included in the Investigator Brochure (IB).

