8.1.1 Study Visits and Assessments

A schedule of study visits and assessments is provided in Table 3 Schedule of Study ActivitiesTable 3

Table 3 **Schedule of Study Activities**

Assessment/Activity	Study Day	Screening Period 48 hrs	Stage 1			Stage 2										Follow Up /ET Day 70
			Ket. Dosing	4 hr	10 hr +2 hours	Day 1	Day 6	Day 7	Day 10	Day 14	Day 21	Day 28	Day 35	Day 42		
						24 hr post dose	+/- 1 day									
Visit Name/No.	Screen	Baseline			1	2	3	4	5	6	7	8	9	10		
Informed Consent		X														
MINI 7.0.2 DSM 5		X														
Demographics		X														
Medical History		X														
Psychiatric History		X														
Physical Exam		X								X				X		
Vital Signs		X	X	X		X		X	X	X	X	X	X	X		
ECG		X				X				X				X		
Concomitant Medications		X	X				X	X	X	X	X	X	X	X		
C-SSRS		X	X	X	X	X	X	X	X	X	X	X	X	X		
Phone Visit*					X		X									
Adverse Events		X	X	X	X	X	X	X	X	X	X	X	X	X		
CHRT—C, SR		X						X		X	X	X	X			
Remote Independent Rater Interview		X**														
CADSS			X	X												
BISS		X	X	X		X		X	X	X	X	X	X	X		
SIBQ			X	X		X		X	X	X	X	X	X	X		
Blood Draw for drug analyses		X				X***				X***				X***		
BARS			X					X	X	X	X	X	X	X		
BPRS			X	X												
PRISE			X	X		X		X	X	X	X	X	X	X		
Chemistry, CBC		X								X				X		
Urine Tox Screen		X								X				X		
Pregnancy Test (Urine)		X								X				X		
Ketamine Infusion			X													
Randomization						X										
Drug Dispensation & Pill Count						X		X		X	X	X	X	X		

*This phone visit should be performed by the site Principal Investigator, or Sub-Investigator. **The independent interview is performed remotely by telephone by independent raters.

***Blood draws for drug analyses 2 hours after the initial dose, prior to administration of NRX-101 on days 14 and 42, and 2 hours after administration of NRX-101 on day 42.

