8.1.6 Randomization

Subjects will be assessed in person 24 hours post-infusion for response to ketamine. Those who do not respond will be provided standard of care for ongoing suicidal ideation. Following the documented observance of a therapeutic response to intravenous ketamine as defined by a 25% or greater reduction in the on the MADRS subset of the BISS score and a score of ≤ 3 on the C-SSRS at 24 hours post infusion, subjects will be randomized 2:1:1 to either a fixed dose combination of experimental drug NRX-101 (DCS + lurasidone), or to an identical capsule containing placebo + lurasidone, or to an identical capsule containing placebo. Randomization blocks will be allocated at the site level to ensure that treatment and control groups are balanced per site. An Interactive Web Response System will be used.

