9.5 Dose Adjustment and Stopping Rules

Subjects will be allowed to titrate up or down, as outlined above, in the event of intolerable side effects. No other dose modifications will be allowed.

Every effort will be made to keep the subject in the study for the full study period consisting of 7 days of acute treatment plus 6 weekly follow-up assessments (Days 10, 14, 21, 28, 35, and 42). Acceptable reasons for early discontinuation include the following: 1) non-response to ketamine treatment, 2) request of subject, 3) decision of physician, 4) SAE, 5) and protocol violation.

A subject who decides to discontinue the investigational product will always be asked about the reason(s) and the presence of any AEs. If possible, they will be seen and assessed by an investigator. Adverse events will be followed up (see Section 12.6) until resolution.

If a subject discontinues from the study before randomization to Stage 2, then no further follow-up will be expected. However, if the subject discontinues after randomization, to Stage 2 but before receiving any study treatment, the subject will be asked to return for a final study visit, during which the procedures outlined in the Early Termination Visit procedures will be completed, including AEs and concomitant medication assessments.

If a subject discontinues from the study before completion of Stage 2 and has received at least 1 dose of study drug, the subject will be asked to return for a final study visit, at which the procedures outlined in the Early Termination Visit will be completed. Every effort will be made to follow up with subjects who discontinue from the study prior to Visit 10 (Day 42). If subjects refuse to return to the clinic for the study-related assessments, a modified follow-up through, for example, regular telephone contact or a contact at study closure will be arranged, if agreed to by the subject and in compliance with local data privacy laws/practices. If the subject refuses follow-up, the reason for the refusal and last contact date will be documented in the eCRF and source documents.

Subjects who discontinue from the study will not be replaced.

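### Section 10.2 describes Kit 1 as a 5-day pack of 10 bottles, while Table 7 in the same section makes it a 7-day pack, which needs 14 bottles

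*Combined protocol and SAP*

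**What the plan says.** Section 10.2 sets a general packing rule: "The bottles will be packaged into a cardboard kit containing 2 bottles for each day". For the starting kit it says: "Kit 1 will contain a 5-day titration pack with 10 bottles, each containing 2 capsules, for the first 5 days of the study". For the dose-change kits it says: "Kits 2 to 5 will contain 3-day step-up or step-down packs with 6 bottles, each containing 2 capsules". Kit 6 is given as a 7-day pack with 14 bottles. The paragraph closes: "A description of the 6 kit types is provided in Table 7".

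Table 7 labels Kit 1 as 7 days and prints seven daily rows. The Day 6 and Day 7 rows each give 475 mg DCS and 33 mg lurasidone morning and evening, or 950 mg and 66 mg per day.

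Three other places bear on which version is meant:

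- Section 4.7 describes "the titration over 5 days to a maximum of 950 mg DCS and 66 mg lurasidone are planned accordingly", and Table 6 shows the same five titration days.
- Section 9.5 describes the study period as "7 days of acute treatment plus 6 weekly follow-up assessments".
- Table 3 has a row "Drug Dispensation & Pill Count". By column position it is marked on Days 1, 7, 14, 21, 28, 35 and 42. It is not marked on Day 6, which is a phone visit.

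**The concern.** Every randomized subject starts on Kit 1, and section 10.2 tells the packager how many bottles to put in it. The sentence and the table cannot both be followed. A kit built to the sentence runs out after Day 5, while Table 3 shows no further dispensing until Day 7. Unless another kit is handed out on Day 1, Day 6 doses would be uncovered, just after the first day at the full daily dose. Section 8.2.5.2.3 treats two missed doses as non-adherence that calls for outreach, so a supply fault could first appear as a compliance problem.

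**Working it through.** **Step 1: the plan's own figures.** The rule is bottles = days × 2 (section 10.2).

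| Kit | Days in text | Bottles in text | Days × 2 | Days in Table 7 |
|---|---|---|---|---|
| 1 | 5 | 10 | 10 | **7** |
| 2 to 5 | 3 | 6 | 6 | 3 |
| 6 | 7 | 14 | 14 | 7 |

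The text is consistent with itself for every kit. Kits 2 to 6 also agree with Table 7 wherever the table is legible. Only Kit 1 conflicts.

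**Step 2: Kit 1 as Table 7 describes it.** 7 × 2 = 14 bottles (28 capsules) against 10 bottles (20 capsules) in the sentence. The difference is 4 bottles, or 8 capsules, which is the supply for Days 6 and 7. Table 7 prints no bottle count, so the 14 is derived. Damage in text extraction does not explain the conflict, because the 7-day label and the two extra daily rows are both legible and agree with each other.

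**Step 3: which version fits the schedule.** Table 3 marks six dispensing days before Day 42 (Days 1, 7, 14, 21, 28 and 35). Assume one kit per dispensing day and no dose changes; the documents do not state this.

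- 7-day Kit 1: 7 + 5 × 7 = 42 days, which is the 6-week treatment period.
- 5-day Kit 1: 5 + 5 × 7 = 40 days, two days short.

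**Step 4: possible shortfall.** Assume packs built to the sentence and only Kit 1 issued on Day 1, so 10 doses are in hand. If both Day 1 bottles are used on Day 1, the doses due by a Day *d* visit are 2(*d* − 1) before that morning's dose and 2(*d* − 1) + 1 after it. If the first bottle is taken on the evening of Day 1 and the sequence runs on from there, one fewer is due. That timing is possible because section 8.1.6 says "Subjects will be assessed in person 24 hours post-infusion for response to ketamine", and randomization follows that assessment. Table 3 prints a window of plus or minus 1 day, and the per-protocol rule in section 6.4 accepts assessments within 1 day through Day 7.

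| Next dispensing visit | Both Day 1 bottles used: due, missed | Evening start: due, missed |
|---|---|---|
| Day 6 | 10–11, 0–1 | 9–10, 0 |
| Day 7 (nominal) | 12–13, 2–3 | 11–12, 1–2 |
| Day 8 | 14–15, 4–5 | 13–14, 3–4 |

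**Step 5: if Kit 6 is also issued on Day 1.** (10 + 14) / 2 = 12 days of supply, so there is no gap.

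**The case against.** The strongest reply is that the 5-day pack may be what is intended. The sentence agrees with itself and with the 5-day titration in section 4.7 and Table 6. Section 9.1 lets physicians raise lurasidone at any point once the initial titration is over, and a 5-day pack followed by Kit 6 or a step kit suits that rule. The mention in section 9.5 of seven days of acute treatment says nothing about pack size. This stands in part: the direction of the error is inferred. The dispensing days in Table 3 still favor the 7-day pack, because a 5-day Kit 1 works only if a second kit is issued on Day 1, and no section says that it is.

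One-kit dispensing also cannot be the general rule. A subject on a 3-day step kit needs 7/3 = 2.33, so three kits, between weekly visits. Section 10.2 leaves kit assignment to the IVRS and does not say which kits, or how many, go out on Day 1. This stands too.

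A reader might therefore infer that the plan leaves subjects without drug on Day 6, or that a fixed share of early doses would be lost. The documents support neither. Both readings need packs built to the sentence and single-kit dispensing, and any count also needs a stated first-dose time and visit day. On the assumptions in the second table, the count runs from 0 to 5.

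Safeguards exist as well: outreach after two missed doses (section 8.2.5.2.3), the Day 6 phone visit (Table 3), and twice-daily contact in the first week for discharged subjects (section 8.1). They should expose a shortage early, but they do not tell the packager which kit to build.

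**Conclusion.** The conflict between the sentence and Table 7 is certain: 5 days and 10 bottles against 7 days and, by derivation, 14 bottles. That the sentence is the wrong one is probable, not established. Any effect on subjects is conditional. With packs built to the sentence and only Kit 1 issued on Day 1, supply ends after Day 5. Day 6 doses are then at risk at a nominal Day 7 visit, with the exact number set by first-dose timing and the visit window. If kits for all three arms were built alike, a shortfall would fall on the arms equally. Alpha, power and sample size do not depend on this. The point is minor, but it concerns a working supply figure and is cheap to put right.

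**What to change.** The sponsor should first confirm which version is intended.

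- **If Table 7 is intended**, reword the sentence along these lines: *Kit 1 is a 7-day pack, the 5-day titration followed by 2 days at the preferred dose, in 14 bottles of 2 capsules, covering Days 1 to 7.*
- **If the 5-day pack is intended**, remove the Day 6 and Day 7 rows from Kit 1 in Table 7, correct its label, and state that Kit 6 is also issued on Day 1.

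In neither case should step-up or step-down kits be held back until the Day 7 visit. Section 9.1 allows a lurasidone increase as soon as the initial titration ends, so a change on Day 6 is permitted.

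If packs already match the intended version, the cost is a wording change plus, in the second case, one dispensing statement. If Table 7 is intended but packs were built to the sentence, each Kit 1 needs 4 more bottles. Assuming one Kit 1 for each of the 124 planned randomized subjects and no overage, that is 4 × 124 = 496 bottles. No visit and no analysis changes.

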10.1.1 Storage

Capsules will be packaged in white HDPE bottles containing desiccant with a PP closure and a foil induction seal. Bottles will be stored at 20°C to 25°C (68°F to 77°F); excursions permitted to 15°C to 30°C (59°to 86°F).

10.1.2 Accountability

The clinical site is required to maintain current drug dispensation and accountability logs throughout the study. All unused supplies will be checked against the drug movement records during the study and/or at the end of the study.

10.1.3 Handling and Disposal

There are no special handling constraints for the IP. Unused IP will be returned to the CRO for disposal.

11. ASSESSMENT OF EFFICACY

The primary outcome measure will be time to relapse, defined as a return to a score of ≥ 4 on the C-SSRS, and/or a score of 20 on the MADRS subset of the BISS. The RAC will adjudicate each site reported instance of relapse for compliance the protocol definition of time to relapse.

Relapse is a time-to-event outcome reflective of this multi-component disorder. Time to relapse is more sensitive measure than an assessment at a fixed time. Time to relapse will be displayed using a Kaplan-Meier lifetable with the treatment groups compared using a two-sided Wilcoxon-Gehan test and a proportional hazard model to include the above cited covariates.

Titration of DCS or lurasidone within the dosing range will not be considered to be a relapse.

All of the instruments used to measure ASIB or depression constitute serial continuous and ordinal outcomes which will be analyzed using MMRM, which accounts for missing data and early discontinuations. These instruments include the following:

- C-SSRS (and the retrospective C-CASA component)
- CHRT (CHRT-SR and CHRT-C)
- BISS
- SIBQ
- BPRS

The models will include treatment group, study visit, the interaction between study visit and treatment group, the baseline of the variable being analyzed, C-SSRS 24 hours post infusion (1, 2), age (<25 yrs, 25-39 yrs, >40 yrs), and gender as fixed effects. The reason for missing data will be evaluated as a condition of MMRM analysis.

Means, mean changes, standard deviations, and ranges will be presented separately for Stage 1 and then for each Stage 2 treatment group over time. These endpoints will be evaluated within the three study treatment groups for the change from Stage 1 and Stage 2 baselines using a paired t-test and between study treatment groups using an unpaired t-test at each time; these p-values will be presented as descriptive statistics.

12. ASSESSMENT OF SAFETY

12.1 Suicidal Ideation and Clinical Management

The documentation and proper management of suicidal ideation by sites will be documented with the use of the Suicidal Ideation and Behavior Questionnaire (SIBQ), completed by site clinicians during all visits, and by remote, independent third party raters during the screening period.

Any subject who, based on the investigator's judgment, poses an imminent risk of suicide should be discontinued from the study (see Section 9.2). All efforts will be taken to minimize the risk of suicide and the investigator will carefully monitor the subject. If during the course of the study, subjects show evidence of suicidal behavior, the subjects will be evaluated immediately or referred to their attending psychiatrist, a local emergency room, or another appropriate clinical setting for further evaluation to see if they are safe to continue in the study. The site will have the ability to direct any subject who requires emergency hospitalization to an emergency room or inpatient psychiatric unit that is within a 50-mile radius of the site. In addition, the subject will be able to contact someone at the site 24 hours a day should they have serious worsening of their condition.

Suicide and attempted suicide, irrespective of the method, but occurring in connection with the use of IP, will be reported as AEs (all suicides are SAEs; attempted suicides can be either serious or non-serious AEs). The event will be identified as suicide or attempted suicide, and the method of the suicide or attempt will be provided. If an attempted suicide meets the criteria for an SAE, the event must be reported according to the guidelines in Sections 12.3 and 12.6.1.1. If a suicide attempt does not meet the criteria for an SAE, it will be considered a reportable AE and a Suicidal Ideation and Behavior Reportable Event Form will be completed by the investigator.

All events of suicidal ideation and behavior will be carefully monitored. These include events of suicide attempts, emergence or significant worsening of suicidal ideation, completed suicides, and suicidal behavior. As described in Section 8.3.5.1.1, the C-SSRS and MADRS items of the BISS, as well as the clinician's judgment, will be used in the assessment of suicidal risk by the investigator. The investigator's clinical judgment and conclusion regarding suicidal risk will be documented in the SIBQ for that visit. Clinically significant (in the opinion of the site investigator) emergence or worsening of suicidal ideation and/or behavior will be considered reportable events and documented as AEs, and a Suicidal Ideation and Behavior Reportable Event Form will be completed and submitted to medical monitor within 24 business hours of the site's knowledge of the ideation or behavior. The subject should be withdrawn from the study and the event will be adjudicated by the RAC as a potential endpoint event.

If suicidal behavior meets the criteria for a SAE, according to the guidelines in Section 12.3, investigators are required to report the event according to the guidelines for SAEs in Sections 12.3 and 12.6.1.1 and submit the completed SAE form to the medical monitor within 24

business hours. The subject should be withdrawn from the study and the event will be adjudicated by the RAC as a potential endpoint event.

The SAE Form will include the exact nature of the event and the circumstances of the subject at the time of the event, in addition to the usual information required to document AEs or SAEs. Data on all of the above will be collected on separate eCRF pages.

The latest version of the AE dictionary, MedDRA, will be used by the CRO for the classification and analysis of AEs entered in the study database. For regulatory reporting, SAEs will be processed in the Electronic Data Capture (EDC) System and coded using MedDRA.

If a subject (or subject's partner) becomes pregnant during the study, it must be reported within 24 business hours of the time the investigator becomes aware of the event and in accordance with the procedures described on the Pregnancy Report Form. Pregnancy in itself is not regarded as an SAE/AE unless there is a suspicion that a study drug may have interfered with the effectiveness of a contraceptive medication. Any pregnancy that occurs from Visit 1 to 30 days following the last dose given will be followed for gestational outcome and the outcome will be reported to the sponsor. The female subject will be discontinued from study medication.

